4.2.16.6 Subgroup Analyses of Exploratory Endpoint

No subgroup analysis.

4.2.16.7 Interim Analysis of Exploratory Endpoint

No presentation for interim analysis.

4.2.17 Exploratory Endpoint - Proportion of SGRQ responders at Week 28 and Week 52

4.2.17.1 Definition

The responders on SGRQ are summarised at Week 28 or Week 52. A change score of 4 units is associated with a minimum clinically important difference (MCID). The responder definition for SGRQ is a decrease of at least 4 score from baseline.

4.2.17.2 Derivations

SGRQ responder (Yes=1/No=0) is calculated on the FAS at each timepoint as follows:

- Responder: Absolute individual change from baseline in total SGRQ score \leq -4
- Non-responder: Absolute individual change from baseline in total SGRQ score > -4

The proportion of responders (non-responders) is calculated as the number of participants who reached the responder (non-responder) SGRQ threshold at each timepoint divided by total number of participants in the FAS.

Strategies of handling intercurrent events are presented in Section 4.2.

4.2.17.3 Handling of Dropouts and Missing Data

No data imputation.

4.2.17.4 Primary Analysis of Exploratory Endpoint

The number and proportions of SGRQ responders, non-responders and missing data are summarised over time on the FAS.

4.2.17.5 Additional Analyses of Exploratory Endpoint

No additional analysis.

4.2.17.6 Subgroup Analyses of Exploratory Endpoint

No subgroup analysis.

4.2.17.7 Interim Analysis of Exploratory Endpoint

No presentation for interim analysis.

4.2.18 Exploratory Endpoint - Change from baseline in AIRQ and proportion of responders at Week 52

4.2.18.1 Definition

AIRQ contains 10 binary questions about respiratory symptoms, activity limitation, sleep, rescue medication use, social activities, exercise, difficulty controlling asthma, and exacerbations. The AIRQ total score change from baseline to Week 52 and the AIRQ

responder rate are calculated at Week 52. The responder definition for AIRQ is a decrease from baseline of at least 2 scores.

4.2.18.2 Derivations

Each positive answer ("Yes") is converted to 1. The AIRQ score for a participant is the sum of all positive answers. A higher score indicates worse asthma control status. If response to any of the questions is missing, the AIRQ is automatically set to missing (directly managed at the data entry level).

The absolute change from baseline in AIRQ score at Week 52 is calculated as described in Section 3.3 on the FAS. Baseline value is derived as presented in Section 3.3.1.2.

Responder (Yes=1/No=0) is calculated at each timepoint as follows:

- Responder: Absolute individual change from baseline in AIRQ score \leq -2
- Non-responder: Absolute individual change from baseline in AIRQ score > -2

The proportion of responders (non-responders) is calculated as the number of participants who reached the responder (non-responder) AIRQ threshold at Week 52 divided by total number of participants in the FAS.

Strategies of handling intercurrent events are presented in Section 4.2.

4.2.18.3 Handling of Dropouts and Missing Data

No data imputation.

4.2.18.4 Primary Analysis of Exploratory Endpoint

The absolute value and absolute change from baseline in AIRQ score at Week 52 are summarised using descriptive statistics. The number and proportions of AIRQ responders, non-responders and missing data at Week 52 are also presented.

The analyses are performed based on the FAS.

4.2.18.5 Additional Analyses of Exploratory Endpoint

No additional analysis.

4.2.18.6 Subgroup Analyses of Exploratory Endpoint

No subgroup analysis.

4.2.18.7 Interim Analysis of Exploratory Endpoint

No presentation for interim analysis.

4.2.19 Exploratory Endpoint - Change from baseline in Sino-nasal Outcome Test (SNOT-22) and responder rate at Week 28 and Week 52

4.2.19.1 Definition

The SNOT-22 is a 22-item health-related outcomes assessment for sinonasal conditions and restricted to participants with history of chronic sinusitis at baseline. Each item is scored as 0 (no problem) to 5 (problem as bad as it can be).

The absolute changes from baseline in SNOT-22 are calculated at Week 28 and Week 52. The responder definition for SNOT-22 is a decrease of at least 8.9 scores from baseline (Hopkins et al, 2009).

4.2.19.2 Derivations

The SNOT-22 score is the sum of the 22 items and it ranges from 0 to 110. Higher scores indicate poorer outcomes. If one or more of the individual items is missing, the total SNOT-22 score is automatically set to missing (directly managed at the data entry level).

The absolute change from baseline in SNOT-22 score at a post-baseline visit is calculated as described in Section 3.3 on the FAS. Baseline value is derived as presented in Section 3.3.1.2.

Responder (Yes=1/No=0) is calculated on the FAS at each timepoint as follows:

- Responder: Absolute individual change from baseline in SNOT-22 score \leq -8.9
- Non-responder: Absolute individual change from baseline in SNOT-22 score > -8.9

The proportion of responders (non-responders) is calculated as the number of participants who reached the responder (non-responder) SNOT-22 threshold at each timepoint divided by total number of participants in the FAS.

Strategies of handling intercurrent events are presented in Section 4.2.

4.2.19.3 Handling of Dropouts and Missing Data

No data imputation.

4.2.19.4 Primary Analysis of Exploratory Endpoint

The absolute values and absolute changes from baseline in SNOT-22 score are summarised using descriptive statistics over time. The number and proportions of SNOT-22 responders, non-responders and missing data are also presented over time. All data available at primary DBL is presented, which includes data beyond Week 28 (see Section 3.1).

The analyses are performed based on the FAS.

4.2.19.5 Additional Analyses of Exploratory Endpoint

No additional analysis.

4.2.19.6 Subgroup Analyses of Exploratory Endpoint

No subgroup analysis.

4.2.19.7 Interim Analysis of Exploratory Endpoint

No presentation for interim analysis.

4.2.20 Exploratory Endpoint - Changes from baseline in Participant Perception of OCS (PPOCS) score at Week 28 and Week 52

4.2.20.1 Definition

The PPOCS questionnaire includes two following questions:

- 1. How bothered are you by the side effects of your current oral steroid dose? The question is asked only at baseline.
- 2. How have the side effects of your current oral steroid dose changed since starting this study? The question is asked at Week 28 and Week 52.

4.2.20.2 Derivations

Response for the first question at baseline is derived as presented in Section 3.3.1.2. The second question already includes the change from baseline. There is no need for additional derivation. Strategies of handling intercurrent events are presented in Section 4.2.

There is no data manipulation required for responses. They are treated as categorical variables.

4.2.20.3 Handling of Dropouts and Missing Data

No data imputation.

4.2.20.4 Primary Analysis of Exploratory Endpoint

The number and percentages of participants selected specific response for each question are presented at baseline, Week 28 and Week 52.

4.2.20.5 Additional Analyses of Exploratory Endpoint

No additional analysis.

4.2.20.6 Subgroup Analyses of Exploratory Endpoint

No subgroup analysis.

4.2.20.7 Interim Analysis of Exploratory Endpoint

No presentation for interim analysis.

4.2.21 Exploratory Endpoint - Mean daily exposure of systemic corticosteroids (mg/day) taken for asthma reasons over 28 and 52 weeks

4.2.21.1 Definition

The mean daily exposure of systemic corticosteroids (SCS; mg/day) taken for asthma reasons is calculated over 28 and 52 weeks. The endpoint allows for an assessment of the overall load of SCS for asthma reasons during the planned treatment period, in addition to maintenance OCS.

4.2.21.2 Derivations

The mean daily exposure of systemic corticosteroids (SCS) taken for asthma reasons is calculated for all participants in the FAS using all SCS medications collected on the ECSYSCRT eCRF page except SCS with a therapy reason of "Non-asthma condition" and "Other". All SCS are converted to a prednisone equivalent dose as described in the CSP Appendix D.

The endpoint is calculated according the following formula:

The mean daily exposure of SCS (mg/day) over 28 (or 52) weeks = Cumulative SCS dose over 28 (or 52) weeks (mg) / minimum(total number of days in the 28-week (or 52) planned treatment period, total number of days from the first IP dose until initiation of another biologic).

where:

Cumulative SCS dose over 28 (or 52) weeks $(mg) = sum \ of \ daily \ SCS \ dose \ over 28 (52)$ weeks of the planned treatment period or earlier if another biologic is initiated.

Strategies of handling intercurrent events are presented in Section 4.2.

4.2.21.3 Handling of Dropouts and Missing Data

No data imputation.

4.2.21.4 Primary Analysis of Exploratory Endpoint

The mean daily exposure of systemic corticosteroids at Week 28 and Week 52 is summarised using descriptive statistics (n, mean, standard deviation, median, minimum and maximum).

In addition, the cumulative SCS dose (mg) is summarised using descriptive statistics (n, mean, standard deviation, median, minimum and maximum) over time on the FAS. The average of the cumulative SCS dose (mg, +/- 1 Standard Error) over the planned treatment

period is presented graphically over time (days). All data available at primary DBL is presented, which includes data beyond Week 28 (see Section 3.1).

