3 DATA ANALYSIS CONSIDERATIONS

3.1 Timing of Analyses

There are 2 database locks (DBLs). The primary DBL carried out after approximately 300 participants completed 28 weeks. All data available at that time is part of the DBL and is analysed with the main focus on estimates of a subset of the pre-planned analysis outputs at Week 28. The final DBL conducted once the last participant completed the safety follow-up visit (Week 64) with the main focus on estimates on Week 52 (end of treatment [EOT]).

An interim analysis (IA) may also be performed as described in Section 5.

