3.3.1 General Study Level Definitions

3.3.1.1 Study period definition

Efficacy analyses are based on planned treatment period, unless otherwise specified. Safety analyses are based on-treatment and/or on-study period.

- Planned treatment period: starts on the date of first dose of IP and ends on the date of the Visit 15 (Week 52) visit or earlier study withdrawal date.
- On-treatment period: starts on date of first dose of IP and ends on earliest(date of last dose of IP + 33 days, date of death, date of study withdrawal). The date of study withdrawal is the completion or discontinuation date from the DISPOSITION eCRF page, where any participant status other than "Completed" has been entered.
- On-study period (planned treatment period and follow-up): starts on the date of first dose of IP and ends on the study completion or withdrawal date.

For analysis performed at primary database lock, the planned treatment period is understood to include all data recorded starting on the date of first dose of IP up until the date of the data cut-off for the primary database lock (details regarding the DCO date and data cleaning can be found in Data Cleaning Requirements for Primary Analysis Lock Plan).

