4.2.21.7 Interim Analysis of Exploratory Endpoint

The derivation of cumulative SCS dose (mg) is presented in Section 4.2.21.2.

The cumulative SCS dose (mg) is summarised over time on the FAS.

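### The by-time mean of cumulative systemic corticosteroid dose (SAP 4.2.21.4) makes no allowance for sums that stop early and does not say who counts on later days

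*SAP*

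**What the plan says.** SAP 4.2.21.2 defines cumulative SCS dose over 28 or 52 weeks as the sum of daily doses over "weeks of the planned treatment period or earlier if another biologic is initiated". SAP 3.3.1.1 says that the planned treatment period "ends on the date of the Visit 15 (Week 52) visit or earlier study withdrawal date"; at the primary database lock it takes in all data "up until the date of the data cut-off for the primary database lock". Starting another biologic does not end the planned treatment period. It is a separate cap on the sum, set in 4.2.21.2.

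SAP 4.2.21.4 then adds the display at issue: "In addition, the cumulative SCS dose (mg) is summarised using descriptive statistics", listed as "n, mean, standard deviation, median, minimum and maximum) over time on the FAS". The average, with one standard error either side, is plotted against days. For the primary lock the section adds: "All data available at primary DBL is presented, which includes data beyond Week 28". SAP 4.2.21.3 allows no imputation. No section says how a participant whose sum has stopped is treated on later days.

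The named endpoint, mean daily exposure, divides the same sum by the participant's own days in the planned treatment period, or by days to another biologic if fewer.

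**The concern.** A cumulative total can be compared between participants only over the same length of follow-up. Here lengths differ, and two programmers could follow the same text and draw different curves.

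- **Stopped sums stay in the mean.** SAP 4.2.21.2 gives an early stopper a defined, non-missing 28- or 52-week total, namely the shorter sum. Carried over to the by-day mean, this counts unobserved time as zero steroid.
- **Only those still observed are averaged.** The mean then moves with who remains. If participants on high doses leave more often, it can even fall from one day to the next, which no cumulative quantity should do.

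Other parts of the SAP do allow for follow-up: exacerbation rates use time at risk (4.2.2.2), adverse event rates are adjusted for exposure (4.6.2.1) and time to OCS reduction is censored (4.2.13.2). This table and graph are an exception. The SAP amendment history says that the table was added to help interpret mean daily exposure, and a display that mixes ended follow-up with reduced steroid use does that poorly.

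**Working it through.** The plan states no figure for cumulative SCS dose, so there is none to reproduce.

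**Inputs from the documents.** The stopping rules are those above. For the cut-off, SAP 3.1 says: "The primary DBL carried out after approximately 300 participants completed 28 weeks". The cut-off therefore shortens sums essentially only after Week 28, and only at the primary lock.

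**Assumed inputs (not in the documents).** Dose of 10 mg/day to day 28, falling linearly to 3 mg/day at day 196, then flat; 5 to 20% leaving evenly by Week 52; uniform accrual over 26, 52 or 78 weeks, with the lock 28 weeks after the last entry.

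**Full follow-up.** Days 1–28: 28 × 10 = 280 mg. Days 29–196: 168 × 10 − 7 × 84.5 = 1,088.5 mg. Days 197–364: 168 × 3 = 504 mg. The total is 1,368.5 mg at Week 28 and 1,872.5 mg at Week 52, where the slope is 3.00 mg/day.

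**Stopped sums kept in the FAS mean.** The mean at day t is Σ dose(u) × F(u) over u ≤ t, where F(u) is the share still followed.

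*Leaving only:* F(u) = 1 − q·u/364, so the shortfall is q × Σ u·dose(u)/364. That is q × 302.3 mg at Week 28 and q × 690.7 mg at Week 52.

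| Leaving by Week 52 (q) | Low at Week 28 | Low at Week 52 | Week 52 slope (mg/day) |
|---|---|---|---|
| 5% | 1.1% | 1.8% | 2.85 |
| 10% | 2.2% | 3.7% | 2.70 |
| 15% | 3.3% | 5.5% | 2.55 |
| 20% | 4.4% | 7.4% | 2.40 |

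*Primary-lock cut-off only:* F(u) = 1 − (u − 196)/(7 × accrual weeks) after day 196. The Week 52 shortfall is 3 × (168 × 169/2)/(7 × accrual weeks) = 42,588/(7 × accrual weeks) mg. There is none at Week 28.

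| Accrual | Observed at Week 52 | Shortfall | Low at Week 52 | Week 52 slope (mg/day) |
|---|---|---|---|---|
| 26 weeks | 8% | 234 mg | 12.5% | 0.23 |
| 52 weeks | 54% | 117 mg | 6.2% | 1.62 |
| 78 weeks | 69% | 78 mg | 4.2% | 2.08 |

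**Only those still observed averaged.** If leaving is unrelated to dose, there is no bias and no flattening from ended follow-up. If leavers take k times the dose of stayers, the Week 52 mean relative to the truth is 1/(1 − q + qk). The last column uses the same inputs for a mean cumulative function, which adds up the daily means of those under observation, each daily mean being dose(u) × [(1 − q) + qk·S(u)]/[(1 − q) + q·S(u)] with S(u) = 1 − u/364.

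| q | k | Still-observed mean | Mean cumulative function |
|---|---|---|---|
| 10% | 1.5 | 1/1.05: 4.8% low | 1.7% low |
| 10% | 2 | 1/1.10: 9.1% low | 3.2% low |
| 10% | 0.5 | 1/0.95: 5.3% high | 1.9% high |
| 20% | 1.5 | 1/1.10: 9.1% low | 3.0% low |
| 20% | 2 | 1/1.20: 16.7% low | 5.6% low |
| 20% | 0.5 | 1/0.90: 11.1% high | 3.7% high |

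A simulation of the same six cases gave still-observed means within about 0.1 percentage point of these.

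**The case against.** A reader might infer that, as written, the curve flattens because follow-up ends and so overstates the fall in steroid load. The documents do not support that. No section says that stopped sums are carried forward on a fixed FAS denominator, and nearby rules lean the other way. SAP 4.2.21.3 bars imputation, SAP 3.2.2 includes withdrawn participants only up to study termination, and SAP 3.3.2 treats a participant with no value in a visit window as missing. The table reports n, and the FAS denominator rule in SAP 3.3 is for proportions. On an available-case reading there is no flattening from this source and the direction of any bias is unknown.

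Those rules do not settle the matter. The window rule concerns assessments at visits rather than a running daily sum, and under 4.2.21.2 an early stopper's total is not missing. The denominator remains open.

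The design also limits the problem. Protocol 7.2 expects withdrawal to be uncommon, Protocol 7.1 offers three follow-up options after tezepelumab is stopped, and Table 6 in Protocol 6.5 prohibits other biologics until the Week 64 follow-up. Nor is this graph the main evidence on steroid sparing. That rests on the primary proportions, the shift tables, the modelled percent change in OCS dose and the Kaplan-Meier analyses. These points stand and keep the matter small.

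**Conclusion.** The gap is real but minor. SAP 4.2.21.4 averages raw sums of unequal length and leaves the by-day denominator open.

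- **If stopped sums are kept,** the curve is always too low: 1.8 to 7.4% at Week 52 with 5 to 20% leaving, and 4.2 to 12.5% at Week 52 of the primary lock from the cut-off alone. The cut-off has no effect at Week 28 or in the final analysis.
- **If only those observed are averaged,** the error is zero when leaving is unrelated to dose. In the informative cases shown it runs from 16.7% low to 11.1% high.

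All of these sizes depend on the assumed dose path, accrual and leaving pattern. They show direction and order of size and do not predict this trial's results. The display supports an exploratory endpoint, and that endpoint is scaled to each participant's own follow-up, so a stopped sum does not shrink it in this way.

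**What to change.** In SAP 4.2.21.4, estimate the curve and the by-time mean as a mean cumulative function. For each day, take the mean SCS dose among FAS participants under observation that day (before withdrawal, another biologic or the data cut-off), then add these daily means up to day t. Use a robust or bootstrap standard error and print the number under observation below the plot. This fixes the denominator and removes the ambiguity.

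Data beyond Week 28 can still be shown at the primary lock, as the SAP does for other endpoints, provided those numbers appear with the curve. SAP 4.2.21.7 uses the same cumulative display ("The cumulative SCS dose (mg) is summarised over time on the FAS"), but its cut-off was planned for mid-April 2023, before this SAP edition of 9 November 2023, so no edit is needed there.

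The cost is a few lines of SAP text and slightly more programming on data already collected. A mean cumulative function still assumes that leaving is unrelated to future dose. In the informative cases above it reduced the error without removing it, leaving it between 5.6% low and 3.7% high.

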4.2.21.5 Additional Analyses of Exploratory Endpoint

No additional analysis.

4.2.21.6 Subgroup Analyses of Exploratory Endpoint

No subgroup analysis.

4.2.21.7 Interim Analysis of Exploratory Endpoint

The derivation of cumulative SCS dose (mg) is presented in Section 4.2.21.2.

The cumulative SCS dose (mg) is summarised over time on the FAS.

4.3 Pharmacodynamic Endpoint

No pharmacodynamic endpoints evaluated in the study.

4.4 Pharmacokinetics Endpoint

No pharmacokinetic endpoints evaluated in the study.

4.5 Immunogenicity

No immunogenicity endpoints evaluated in the study.

4.6 Safety Analyses

Safety and tolerability of tezepelumab is assessed from serious adverse events (SAEs), SAEs with outcome of death, adverse events leading to discontinuation of IP (DAEs), adverse events of special interest (AESIs), and laboratory test results. All safety variables are summarised using the FAS.

4.6.1 Exposure

4.6.1.1 Definitions and Derivations

Extent of exposure to IP is defined as the number of days between the date of first dose of IP and the date of last dose of IP inclusive plus the number of days allowance for the dosing interval specified in Section 3.3.1.1, that is:

```
Extent of exposure (days) = earliest(date of last dose of IP + 33 days; date of death; date of study withdrawal) – date of first dose of IP + I
```

This calculation does not consider any gaps in exposure caused by the participant missing one or more intermediate scheduled 4-weekly doses. Such cases are identified in the CSR if they occur but are not explicitly accounted for in any analysis.

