Important protocol deviations will be defined prior to first participants enrolled. Participants will not be excluded from analysis sets on the basis of any important protocol deviations. The definitions of each category of important protocol deviation will be fully specified in the SAP. Details regarding statistical analysis will be provided in the SAP. In general, continuous endpoints will be summarised using the mean, the standard deviation, median, minimum value, and maximum value, and the categorical endpoints will be summarised using frequency counts and percentages. Two-sided 95% CI for proportions computed using exact Clopper-Pearson method may also be presented. Time to event data will be presented graphically using Kaplan Meyer curve.

In general, all data up to Week 28 or Week 52 will be included in the analysis, even if a participant discontinues treatment or changes background therapy other than OCS (treatment policy strategy). If a participant initiates therapy with other biologic for treatment of asthma, then only data collected up until the initiation of the other biologic treatment will be included in the analysis (hypothetical strategy).

In general, efficacy analyses will be based on planned treatment period, starting on the date of first dose of IP and ending on the date of the Week 28 or Week 52 visit or earlier study withdrawal date.

Safety analyses will be based on-treatment and/or on-study period. Details will be specified in the SAP. On-treatment period starts on the date of first dose of IP and ends on minimum (date of last dose of IP + 33 days, date of death, date of study withdrawal). On-study period (planned treatment and follow-up) starts on the date of first dose of IP and ends on the study completion or withdrawal date. Data will be listed in participant-level data listings.

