4.6.2 Adverse Events

4.6.2.1 Definitions and Derivations

Adverse events, categorised as Serious Adverse Events (SAEs), SAEs with outcome of death, Adverse Events leading to discontinuation of IP (DAEs), Adverse Events of special interest (AESIs) defined in the CSP Section 8.3.6, experienced by the participants were collected throughout the entire study and coded using the latest version of the Medical Dictionary for Regulatory Activities (MedDRA).

Adverse event data is categorized according to their onset date into the following study periods:

- AEs in the pre-treatment period are defined as those with onset day before day of first dose of study treatment.
- AEs in the on-treatment period are defined as those with onset day between the day of first dose of study treatment and earliest (date of last dose of IP + 33 days, date of death, date of study withdrawal).
- AEs in the post-treatment period are defined as those with onset after the end of ontreatment period defined above until the study completion or withdrawal date.
- AEs in the on-study period are defined as those with onset between day of first dose of study treatment and the study completion or withdrawal date.

If an AE has a missing onset date completely it is considered an on-treatment event unless the stop date of the AE indicates otherwise. Similarly, if an AE has a partial onset date it is considered an on-treatment AE unless the partial onset date or the stop date indicates otherwise.

AEs that have missing causality (after data querying) is assumed to be related to study drug.

Liver adverse events and evaluation of Hy's Law are submitted as a SAE and is described accordingly. Hy's Law cases are listed with their related laboratories parameters. Details regarding Potential Hy's Law and Hy's Law are given in the CSP Appendix F2.

Adjusted incidence rate

Exposure-adjusted incidence rate is defined as the total number of participants reporting adverse events experienced during the extent of exposure divided by total extent of exposure (irrespective of whether they have had the AE). The individual participant' extend of exposure (days) is calculated as presented in Section 4.6.1.1. The total participant-years

exposure is derived as the sum of the individual participant extent of exposure (days) divided by 365.25.

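### Extent of exposure has no data cut-off term, so any exposure-adjusted safety rate run at the Week 28 lock would be a few percent too low

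*SAP*

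**What the plan says.** SAP 4.6.1.1 counts extent of exposure from the first dose, inclusive, to "earliest(date of last dose of IP + 33 days; date of death; date of study withdrawal". SAP 3.3.1.1 closes the on-treatment period with the same three terms: it "ends on earliest(date of last dose of IP + 33 days, date of death, date of study withdrawal". Protocol 9.4.1 agrees: the period "ends on minimum (date of last dose of IP + 33 days, date of death, date of study withdrawal". None of these names a data cut-off.

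SAP 4.6.2.1 defines the exposure-adjusted incidence rate as the number of participants with an event during the extent of exposure, "divided by total extent of exposure (irrespective of whether they have had the AE". SAP 4.6.2.2 plans such tables for SAEs and for AESIs and does not confine them to one lock.

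The only cut-off rule is in SAP 3.3.1.1. For the primary lock, "the planned treatment period is understood to include all data recorded starting on the date of first dose of IP" up to the cut-off date. That period serves efficacy. For safety the same section says "Safety analyses are based on-treatment and/or on-study period".

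On timing, SAP 3.1 says of the primary lock: "All data available at that time is part of the DBL and is analysed with the main focus on estimates". The sentence goes on to refer to a subset of the planned Week 28 outputs, which is not listed.

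**The concern.** Dosing continues every four weeks to Week 48, but the primary lock comes when about 300 participants have reached Week 28. Take a participant who has neither died nor withdrawn and whose last recorded dose is less than 33 days before the cut-off. The formula carries that participant's exposure past the cut-off. The locked data cannot contain events from those days, so the numerator and the denominator of the rate cover different time.

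The error has one direction: exposure is too long and the rate too low. The trial has a single arm, so there is no comparator in which the same error would cancel. The descriptive summary of exposure days is inflated in the same way.

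The SAP handles this point elsewhere. The planned treatment period is bounded at the cut-off for the primary lock, and exacerbation time at risk over 28 weeks (SAP 4.2.2.2, Table 5) is tied to visit or assessment dates.

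**Working it through.** The documents give no exposure total, event count or safety rate to reproduce. The one figure that can be checked is the 33-day allowance.

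**Inputs from the documents**
- End of exposure: SAP 4.6.1.1.
- Doses every 28 days from Week 0 to Week 48, that is Days 1, 29, …, 337: Protocol 1.1.
- End-of-treatment visit four weeks ± 5 days after the last dose: Protocol 1.3.
- Primary lock after about 300 participants complete 28 weeks: SAP 3.1.

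**Assumptions, because the documents are silent:** 300 participants; even accrual over 12 to 104 weeks; doses on schedule; cut-off on the day the last entrant reaches Week 28; 0% to 20% early discontinuation of treatment.

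**1. The allowance.** 28 + 5 = 33 days, so it equals one dosing interval plus the visit window.

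**2. One participant, last dose at Week 28 (Day 197).** Credited days = 197 + 33 = 230. Truncated days = min(230, cut-off day). The rate shortfall is 1 − truncated/credited.

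| Cut-off after last dose | Truncated days | Excess days | Exposure too high | Rate too low |
|---|---|---|---|---|
| same day | 197 | 33 | 16.8% | 14.3% |
| 14 days | 211 | 19 | 9.0% | 8.3% |
| 27 days | 224 | 6 | 2.7% | 2.6% |

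**3. Average excess.** If the time since the last dose is spread evenly over 0 to 27 days, its mean is 13.5 and the mean excess is 33 − 13.5 = 19.5 days. A simulation that also includes participants just past their final dose gives about 19 days.

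**4. Whole cohort, no early discontinuation** (simulated; percentages taken before the participant-years were rounded).

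| Accrual | Credited participant-years | Truncated participant-years | Exposure too high | Rate too low |
|---|---|---|---|---|
| 12 weeks | 211.8 | 195.7 | 8.2% | 7.6% |
| 26 weeks | 250.5 | 235.5 | 6.3% | 6.0% |
| 52 weeks | 276.9 | 269.4 | 2.8% | 2.7% |
| 78 weeks | 285.9 | 280.8 | 1.8% | 1.8% |
| 104 weeks | 290.1 | 286.3 | 1.3% | 1.3% |

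Hand check of the 52-week row: 48% of participants carry future time, averaging 19.1 days. Then 300 × 0.48 × 19.1 / 365.25 = 7.5 participant-years, and 269.4 + 7.5 = 276.9.

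**5. Early discontinuation of 20%.** The rate shortfall becomes 7.1%, 5.5%, 2.5% and 1.2% for accrual of 12, 26, 52 and 104 weeks. Discontinuation therefore matters little.

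**6. Illustration.** Suppose 24 participants have an SAE (an assumed count) with 52-week accrual. The formula gives 100 × 24/276.9 = 8.67 per 100 participant-years, against 100 × 24/269.4 = 8.91 with truncation.

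**7. Other analyses.** At the final lock, Day 337 + 33 = Day 370 falls before the Week 64 contact (64 × 7 + 1 = Day 449), so no future time is credited. For adverse events at the interim analysis, SAP 4.6.2.2 plans counts, percentages and key subject information, with no exposure-adjusted rates.

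**The case against.** The strongest objection is that the documents do not place these tables at the primary lock. SAP 3.1 speaks of an unlisted subset of outputs, and SAP 4.6.2.2 assigns the exposure-adjusted tables to no particular lock. SAP 3.3.1.1 also sends cut-off details to a separate data-cleaning plan that is not available here, so a truncation rule in that plan or in the programming cannot be excluded. Both points stand. They make the effect conditional on the tables being run, but they do not mend the formula. The SAP cites that plan for the cut-off date and data cleaning, whereas the derivation of exposure belongs in the SAP.

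A second objection is that the on-treatment period is already bounded in practice. The windowing rules in SAP 3.3.2 first select records in the planned treatment period and then flag those that are on treatment. That is right for records: no event after the cut-off can enter a count. Extent of exposure is date arithmetic, not a selection of records, so this does not limit it.

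Third, the measure is openly approximate. SAP 4.6.1.1 ignores missed doses, and SAP 4.6.2.1 keeps exposure after a first event. The study is descriptive, and Protocol 4.2 expects no meaningful new safety information from it. This limits the importance of the error, but those conventions are declared and this one is not.

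A reader might infer that all Week 28 safety results, or the trial's final safety rates, are biased. The documents do not support that. Crude numbers and percentages of SAEs, DAEs and AESIs do not use this denominator, and by the final lock every 33-day allowance has run out.

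**Conclusion.** The formula in SAP 4.6.1.1 is wrong as written for use at the primary lock. Any exposure summary or exposure-adjusted SAE or AESI rate produced then credits participants still on treatment with about 19 days beyond the cut-off on average. The direction is certain. The size depends on accrual: for assumed even accrual of 12 to 104 weeks, exposure is about 8% down to 1% too high and the rates are too low by about the same.

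The 17% figure should not be read as a cohort result. It is the limit for a participant dosed at Week 28 on the cut-off day, and it would apply to the cohort only if everyone were in that position. The effect is modest and confined to one lock, and whether the tables are run then is likely but not confirmed. It is still worth correcting, because it is avoidable and always favours the drug.

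**What to change.** For the primary lock, add the data cut-off date as a fourth term in the earliest-of list in SAP 4.6.1.1, next to last dose plus 33 days, death and study withdrawal. This is the only change that alters a result.

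For consistency, add the same term to the on-treatment definitions in SAP 3.3.1.1 and 4.6.2.1, where it changes no event count. It would also help to state which exposure and adverse event outputs belong to the primary lock.

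The cost is one term in each definition and no new data. Under the accrual assumptions above, primary-lock exposure becomes a few percent smaller. The final analysis is unchanged.
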